6.3.1 General dose modification instructions for PDR001 or placebo

No dose reductions are allowed for PDR001. Dose interruption for PDR001/placebo includes delaying or withholding the treatment for any reason as well as an interruption of treatment during an infusion. Subjects with adverse events suspected to be related to PDR001 or placebo including those of potential immune-mediated etiology (irAE) (see definition in [Section 6.3](#)) must be permanently discontinued from PDR001 or placebo if (1) the AE doesn't recover to ≤ Grade 1 or baseline within 12 weeks and/or (2) the dose of steroids (for the management of irAE) remains > 10 mg/day prednisone or equivalent for >12 weeks.

The 12 week timeframe will begin from the time the irAE reaches a grade that leads to PDR001/placebo interruption.

Subjects who discontinue the study for a study related adverse event or an abnormal laboratory value must be followed as described in [Section 7](#).

6.3.2 General dose modification instructions for dabrafenib and trametinib:

[figure not shown]
If treatment related toxicities occur that are specific to combination treatment of dabrafenib and trametinib, then both treatments should be simultaneously dose reduced, interrupted or discontinued with the exceptions shown below:

Exception where dose modification is necessary for **only dabrafenib**:

- Uveitis ([Table 6-25](#))

Exception where dose modifications are necessary for **only trametinib**:

- Retinal vein occlusions (RVO) ([Table 6-25](#)) and retinal pigment epithelial detachment (RPED) ([Table 6-26](#))
- Left ventricular ejection fraction (LVEF) reduction ([Table 6-22](#))

If a subject’s dose of dabrafenib and trametinib has been reduced per the dose modification instructions, re-escalation of the subject’s dose is recommended provided the following criteria are met:

- a period of 4 weeks of treatment has passed since restarting dosing at the lower dose level and there is no recurrence of the AE
- the subject is deriving clinical benefit

For dabrafenib and/or trametinib related adverse events: if following an interruption of dabrafenib and trametinib, an AE doesn’t recover to ≤ Grade 1 or baseline within 4 weeks, dabrafenib and trametinib must be discontinued.

6.3.3 Dose modification and management guideline for adverse events common to PDR001, dabrafenib and trametinib

Adverse events that have been reported with PDR001, dabrafenib or trametinib include, but are not limited to diarrhea/colitis, abnormal liver enzymes, skin rash, nephritis, pneumonitis, encephalitis, and endocrinopathies. It is possible that these and /or other adverse events may be exacerbated when PDR001, dabrafenib and trametinib are combined. Therefore, it is important to note that the management guidelines for the combination of PDR001, dabrafenib and trametinib may differ for a given AE from the management guidelines for each agent or combination treatment of dabrafenib and trametinib.

6.3.3.1 Mandatory dose modifications and recommended clinical management guidelines for diarrhea/colitis

Guidelines for dose modification and management for diarrhea and colitis considered to be related to study treatment by the investigator are provided in [Table 6-9](#).

Table 6-9 Mandatory dose modifications and recommended clinical management guidelines for diarrhea/colitis

CTCAE v4.03	Recommended adverse event management guidelines	Mandatory dose modification requirements
Grade 1 diarrhea (increase of <4 stools per day over baseline; mild increase in ostomy output compared to baseline) OR Grade 1 colitis (asymptomatic; clinical or diagnostic observations only; intervention not indicated) OR Grade 2 diarrhea (increase of 4 - 6 stools per day over baseline; moderate increase in ostomy output compared to baseline) OR	
 • Diet: stop all lactose containing products; eat small meals, BRAT diet (banana, rice, apples, toast) • Hydration: 8-10 large glasses of clear liquids per day (e.g., Gatorade or broth) • Loperamide: initially 4 mg, followed by 2 mg every four hours or after every unformed stool; maximum 16 mg/day. Continue until diarrhea free for 12 hours; • Diarrhea > 24hr: loperamide 2 mg every two hours; maximum 16 mg/day. Consider adding oral antibiotics. • Diarrhea > 48hr: loperamide 2 mg every two hours; maximum 16 mg/day. Consider other 	
 • Continue PDR001/placebo, dabrafenib and trametinib at the same dose level. • If diarrhea is Grade 2, despite loperamide at 2 mg every two hours for > 48hr: • Interrupt PDR001/placebo, dabrafenib and trametinib until ≤ Grade 1, and then reinstate PDR001, dabrafenib and trametinib at the same dose level.

CTCAE v4.03	Recommended adverse event management guidelines	Mandatory dose modification requirements
Grade 2 colitis (abdominal pain; mucus or blood in stool)	
second-line therapies for diarrhea (e.g., octreotide, oral diphenoxylate, and oral antibiotics)
 
 • If Grade 2 and no improvement in 5 days consider oral steroids • If Grade 2 diarrhea persists >1 week consider gastroenterologist consultation and endoscopy to evaluate for colitis • If Grade 2 persists for 5 days and worsening of symptoms or diffuse ulcerations and bleeding seen on endoscopy, commence oral steroids at a dose 0.5 to 1 mg/kg/day prednisone equivalents and continue until symptoms improve to Grade 1. If no improvement occurs, manage as per Grade 3. Steroids can be tapered as per Section 6.3.4.1. • Lower GI endoscopy and biopsy should be considered and may assist in determining the duration of steroid taper based on the evidence of macroscopic and microscopic inflammation. 	

Grade 3 diarrhea (increase of ≥ 7 stools per day over baseline; incontinence; hospitalization indicated; severe increase in ostomy output compared to baseline; limiting self-care ADL) OR Grade 3 colitis (severe abdominal pain; change in bowel habits; medical intervention indicated; peritoneal signs)
	
 • Clinical evaluation and hospitalization mandatory; rule out bowel perforation and intravenous hydration. • Consider consultation with gastroenterologist and confirmation biopsy with lower GI endoscopy. • In addition to symptomatic treatment (diet, hydration, loperamide, antibiotics if indicated); initiate immediate treatment with intravenous steroids (methylprednisolone 1mg/kg/day) followed by high dose oral steroids (1 to 2 mg/kg/day prednisone equivalents) • When symptoms improve to \leq Grade 1, steroid taper should be started and continued over no less than 4 weeks as per Section 6.3.4.1. • Taper over 6 to 8 weeks in subjects with diffuse and severe ulceration and/or bleeding. • If no improvement in 2-3 days: consider initiating infliximab 5 mg/kg and continue steroids. 	
1st occurrence
 
 • Interrupt PDR001/placebo, dabrafenib and trametinib until \leq Grade 1, and then reinstate PDR001 treatment (after appropriate steroid tapering) and reduce dabrafenib and trametinib to the next lower dose level per Table 6-7. Re-escalation of the subject's dose is recommended if criteria in Section 6.3.2 are met. • AE resolution to \leq Grade 1 or baseline must occur within a period of 12 weeks since a grade 3 event has been identified, otherwise PDR001 must be permanently discontinued. 
2nd occurrence
 
 • Permanently discontinue PDR001/placebo. • Interrupt dabrafenib and trametinib until \leq Grade 1, and then reduce dabrafenib and trametinib to the next lower dose per Table 6-7. Re-escalation of the subject's dose is recommended if criteria in Section 6.3.2 are met. 
3rd occurrence

CTCAE v4.03	Recommended adverse event management guidelines	Mandatory dose modification requirements
	
(Infliximab is contraindicated in subjects with sepsis or a perforation). Upon symptomatic relief initiate a prolonged steroid taper over 45 to 60 days.
 
 If symptoms worsen during steroid reduction, initiate a re-tapering of steroids starting at a higher dose followed by a more prolonged taper and administer infliximab. If symptoms persist despite the above treatment, a surgical consult should be obtained. 	
 Permanently discontinue dabrafenib and trametinib.
Grade 4: Life-threatening consequences; urgent intervention indicated	
 Same as Grade 3 	
 Permanently discontinue PDR001/placebo, dabrafenib and trametinib.

6.3.3.2 Mandatory dose modifications and recommended clinical management guidelines for abnormal liver enzyme test

Guidelines for dose modification and management of abnormal liver enzyme functions considered to be related to study treatment by the investigator are provided in [Table 6-10](#).

In addition to the instructions below, subjects with normal baseline transaminases and bilirubin who experience sudden elevations even within Grade 1, should be monitored more closely.

Table 6-10 Mandatory dose modifications and recommended clinical management guidelines for abnormal liver enzyme test

Abnormal liver enzyme tests/hepatitis		
Grade	Recommended adverse event management guidelines	Mandatory dose modification requirements
Grade 2: AST or ALT >3× ULN to ≤ 5× ULN and/or bilirubin > 1.5× ULN to ≤ 3× ULN	
 Monitor hepatic laboratory tests more frequently (every 2-3 days) until returned to baseline values 	
 Interrupt PDR001/placebo, dabrafenib and trametinib until ≤ Grade 1, and then reinstate PDR001/placebo, dabrafenib and trametinib at the same dose level.
Grade 3 or 4: AST or ALT > 5× ULN and/or bilirubin > 3× ULN	
 Monitor hepatic laboratory tests more frequently (every 2-3 days) until return to baseline values. Consider appropriate consultation* with hepatologist and liver biopsy to establish etiology of hepatic injury, if necessary If after 2-3 days new liver assessment shows worsening of laboratory test consider to initiate treatment with high dose steroids (1 to 2 mg/kg/day prednisone or equivalents) 	
 Permanently discontinue PDR001/placebo only if causality is suspected to be related to PDR001/placebo ** If lab results show worsening, follow the management and dose modification (instructions below) 
1st occurrence
 
 Interrupt dabrafenib and trametinib until recovery to ≤ Grade 1 or baseline 
 Reduce dabrafenib and trametinib to the next lower dose level per Table 6-7. Re-escalation of the subject's

Abnormal liver enzyme tests/hepatitis

Grade	Recommended adverse event management guidelines	Mandatory dose modification requirements
	
 Add prophylactic antibiotics for opportunistic infections Start steroid taper as outlined in Section 6.3.4.1 if symptoms improve to Grade ≤ 1 If serum transaminase levels do not decrease 48 hours after initiation of systemic steroids, oral mycophenolate mofetil 500 mg every 12 hours may be given. Infliximab is not recommended due to its potential for hepatotoxicity 	
dose is recommended if criteria in Section 6.3.2 are met.
 
 If no recovery to \leq Grade 2 within 10 weeks, permanently discontinue dabrafenib and trametinib. 
2nd occurrence
 
 Interrupt dabrafenib and trametinib until \leq Grade 1. Reduce dabrafenib and trametinib to the next lower dose level per Table 6-7. Re-escalation of the subject's dose is recommended if criteria in Section 6.3.2 are met. 
3rd occurrence
 
 Permanently discontinue dabrafenib and trametinib

*Rule out viral hepatitis and other potential causes of liver injury

**For patients with liver metastasis who begin treatment with Grade 2 AST or ALT, if AST or ALT increase by $\geq 50\%$ relative to baseline and last for at least 1 week then the patient should be discontinued

Note: For additional information on follow-up of potential drug induced liver injury cases, refer to [Section 6.3.6.2](#).

[figure not shown]

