6.3 Dose modifications and reductions

Adverse events of special interest (AESI) include AEs of a potential irAE that are associated with PDR001 treatment. An irAE may be experienced by subjects treated with PDR001 due to its mechanism of action and predicted based on the reported experience with other immunotherapies that have a similar mechanism of action. Investigators must be vigilant and carefully identify AEs that may be suggestive of potential irAEs as their appearance may be sub-clinical and early diagnosis is critical for its adequate management and resolution.

An irAE is typically low grade and self-limited, often occurring after multiple doses, and most frequently involving the GI tract (diarrhea/colitis), skin (rashes), liver (hepatitis), lung (pneumonitis), kidneys (nephritis) and endocrine systems (a variety of endocrinopathies) and rarely CNS (encephalitis). Serological, immunological and histological assessments should be performed as deemed appropriate by the investigator, to verify the potential immune-related nature of the AE, and exclude a neoplastic, infectious or metabolic origin of the AE.

Severe grade or persistent lower grade irAEs typically require interrupting or permanently discontinuing treatment and administration of systemic steroids or other non-corticosteroid immunosuppressive medication when systemic steroids are not effective. Early recognition of irAEs and initiation of treatment are critical to reduce the risk of complications, since the majority of irAEs are reversible with the use of steroids and other immune suppressants.

In some cases, it may be unclear to determine if an adverse event is immune related or not, thus the following dose reduction guidelines should be followed.

The following sections address the specific instructions for mandatory dose modifications and recommended management for AEs considered suspected to be related to study treatment. For subjects who do not tolerate the protocol-specified dosing schedule, dose interruptions or modifications are mandated in order to allow subjects to continue study treatment.

No dose reductions are allowed for PDR001. Dose interruption for PDR001/placebo includes delaying or withholding the treatment for any reason as well as an interruption of treatment during an infusion. All dose interruptions and the reason for the dose interruption must be

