Trial participants who have been exposed to someone infected by COVID-19 and/or who develop symptoms indicative of potential COVID-19 infection (see above) should contact the Investigator and discuss the next steps; these may include self-quarantine, or may require further testing/follow-up as appropriate. Administration of the study treatment may be delayed based on the risk benefit assessment until the trial participant completes the quarantine and remains asymptomatic and/or COVID-19 infection has been ruled out. Investigators are recommended to follow the local health authority guidelines for prevention against COVID-19.

[figure not shown]
[figure not shown]

Table 6-7 Dose modification steps for PDR001/placebo, dabrafenib and trametinib

Dose modification for PDR001 or placebo ^a				
	Starting dose level	Dose level - 1		
PDR001 or placebo	400 mg Q4W 400 mg Q8W (only if DL-1a is determined to be the dose regimen)	Not applicable		
Dose reduction for dabrafenib ^{a, b}				
	Starting dose level	Dose level - 1	Dose level - 2	Dose level - 3
Dabrafenib	150 mg BID (300 mg/day)	100 mg BID (200 mg/day)	75 mg BID (150 mg/day)	50 mg BID (100 mg/day)
Dose reduction for trametinib ^{a, b}				
	Starting dose level	Dose level - 1	Dose level - 2	Dose level - 3
Trametinib	2 mg QD	1.5 mg QD	1.0 mg QD	-
Q4W: once in every 4 weeks; BID: twice daily; QD: once daily				
^a . Dose modification should be based on the worst toxicity demonstrated at the last dose.				
^b . Dose reduction below 50 mg BID for dabrafenib and 1.0 mg QD for trametinib are not allowed.				

Table 6-8 Reference of AEs and toxicity management guidelines

Adverse Events	PDR001	dabrafenib	trametinib	Guideline
Diarrhea/colitis	X	X	X	Section 6.3.3.1 Table 6-9.
Abnormal liver enzyme test	X	X	X	Section 6.3.3.2 Table 6-10.
Skin rash	X	X	X	Section 6.3.3.3 Table 6-11.
Serious skin reaction	X	X	X	Section 6.3.3.4
Nephritis	X	X	X	Section 6.3.3.5 Table 6-12
Pneumonitis	X	X	X	Section 6.3.3.6 Table 6-13
Encephalitis	X	X	X	Section 6.3.3.7 Table 6-14
Endocrine events	X	X	X	Section 6.3.3.8 Table 6-15
Hand foot skin reaction	X	X	X	Section 6.3.3.9 Table 6-16
Neutropenia and thrombocytopenia	X	X	X	Section 6.3.3.10 Table 6-17
Adverse events including abnormal laboratory related AEs	X	X	X	Section 6.3.3.11 Table 6-18
Asymptomatic amylase and/or lipase elevation	X	X	X	Section 6.3.3.11 Table 6-18
Others	X	X	X	Section 6.3.3.12 Table 6-19
Infusion reaction and cytokine release syndrome	X			Section 6.3.4 Table 6-20

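### Table 6-9 gives Grade 2 colitis no mandatory PDR001 hold of its own; the row's only trigger is loperamide-resistant Grade 2 diarrhea

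*Protocol*

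**What the plan says.** Table 6-9 has one combined row for Grade 1 diarrhea, Grade 1 colitis, Grade 2 diarrhea and Grade 2 colitis. The last entry is defined by its own symptoms: "Grade 2 colitis (abdominal pain; mucus or blood in stool".

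The mandatory column for that row opens with "Continue PDR001/placebo, dabrafenib and trametinib at the same dose level". It then gives one condition for interrupting the three drugs: "If diarrhea is Grade 2, despite loperamide at 2 mg every two hours for > 48hr". Colitis is not named there.

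The recommended column of the same row has steroid steps. The earliest is "If Grade 2 and no improvement in 5 days consider oral steroids". A firmer step starts prednisone-equivalent 0.5 to 1 mg/kg/day when Grade 2 lasts 5 days with worsening symptoms, or when endoscopy shows diffuse ulceration and bleeding. If that fails, the event is managed as Grade 3.

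Three general provisions bear on the row:

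- Table 6-8 assigns diarrhea/colitis to "Section 6.3.3.1 Table 6-9".
- Section 6.3 states: "Severe grade or persistent lower grade irAEs typically require interrupting or permanently discontinuing treatment". It also mandates interruption or modification for subjects who cannot tolerate the dosing schedule.
- Section 6.3.1 requires permanent discontinuation of PDR001/placebo if a related event has not recovered within 12 weeks, and dates that period as follows: "The 12 week timeframe will begin from the time the irAE reaches a grade that leads to PDR001/placebo interruption".

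**The concern.** A loperamide-failure test suits stool frequency. It does not suit pain, mucus or bleeding. A subject can meet the Grade 2 colitis definition without Grade 2 diarrhea, and the column headed as mandatory then tells the site to carry on with an anti-PD-1 antibody. Whether the next infusion is given depends on general text and on the investigator.

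The protocol itself treats colitis as important. Section 1.2.1.2 reports one serious adverse event suspected to be related to PDR001 in the first-in-human study, a Grade 3 autoimmune colitis. Section 2.6 lists diarrhea/colitis among the overlapping toxicities of the three drugs.

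The secondary concern is the stopping rule. If no grade-based interruption applies, the start of the 12-week limit is not stated.

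**Working it through.** There is no plan figure to reproduce. The check sets the texts side by side and adds a little arithmetic on exposure.

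**1. Routes to a PDR001 hold for Grade 2 colitis without persistent Grade 2 diarrhea**

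| Route | Source | Mandatory and specific to colitis? |
|---|---|---|
| Hold trigger in the row | Table 6-9, mandatory column | No; written for diarrhea only |
| Dosing schedule not tolerated | Section 6.3 | Mandatory, but general |
| Persistent lower-grade irAE | Section 6.3 | General; describes what is typical |
| Withholding for any reason | Section 6.3.1 | Discretionary |
| Steroids above 10 mg/day | Section 6.4.3.1 | Mandatory once steroids are given; not tied to colitis |
| Managed as Grade 3 | Table 6-9, recommended column | Only after steroids fail |

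On the steroid route, 0.5 mg/kg/day × 20 kg = 10 mg/day. The firm steroid step therefore exceeds the limit in any adult above 20 kg and bars the next infusion until taper. Within the row, however, no steroid step comes before 5 days.

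**2. Grade 2 in the other graded non-hematologic tables of Section 6.3.3**

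- Outright PDR001 hold: Tables 6-10 (liver), 6-12 (renal), 6-13 (pneumonitis), 6-14 (encephalitis) and 6-19 (other events of special interest). That is 5. The liver row interrupts until Grade 1 or lower "and then reinstate PDR001/placebo, dabrafenib and trametinib at the same dose level".
- Conditional hold tied to the event: Tables 6-11 (rash, if intolerable), 6-16 (hand-foot reaction, no improvement within 7 days or recurrence) and 6-18 (other events, if intolerable). That is 3.
- Total: 5 + 3 = 8 of 8.

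Outside that set, Table 6-17 continues PDR001 for Grade 2 cytopenias. Table 6-20 (Section 6.3.4) continues it with premedication at the first Grade 2 infusion reaction and only suggests considering discontinuation at the second; its stop-infusion advice is in the recommended column. Counting Table 6-20 makes it 8 of 9.

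**3. The 12-week clock**

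Table 6-9 states a 12-week limit only in its Grade 3 row, counted from a Grade 3 event. For a Grade 2 colitis the text allows four readings: (a) onset of Grade 2; (b) start of steroids; (c) the undated point at which it is managed as Grade 3; (d) no start, because no Grade 3 event was identified. If the row's own steps are followed, (a) and (b) differ by at least 5 days, and the distance to (c) is not bounded.

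Tables 6-12, 6-13 and 6-14 count from the Grade 2 event. Other rows are uneven too: Grade 2 liver and hand-foot reaction state no clock, and the Grade 2 rash row counts from a Grade 3 event.

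**4. Size**

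- Chance that a Q4W infusion falls due in the 5 days before the row's earliest steroid step: 5/28 = 0.179, or 18%. This assumes that such an episode occurs, that onset is uniform over the 28-day cycle, that the investigator does not hold, and that no early steroids are given (Section 6.4.1 permits them). The protocol gives no frequency for such episodes.
- Subjects on treatment at Amendment 7: 2 + 1 + 88 = 91. Fewer were on PDR001, because placebo infusions had been stopped (Section 4.1.2).
- Time left: 5 years from the last randomization, taken as between 8 June and 11 July 2018 (the last randomized subject's first visit and first treatment), ends between 8 June and 11 July 2023. From 27 January 2023 that is 132 to 165 days; 132/28 = 4.7 and 165/28 = 5.9 cycles.

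**The case against.** The strongest reply is that the episode is already covered. Section 6.3 mandates interruption for subjects who do not tolerate dosing. That tolerability judgement is the same kind that counts as a hold in Tables 6-11 and 6-18, and the intolerable-Grade-2 row of Table 6-18 could be read to include colitis. Worsening disease brings steroids, and steroids block the infusion. What remains is a tolerated, non-worsening Grade 2 colitis, not on steroids, with an infusion falling due. An investigator who does withhold can reasonably be taken to have started the 12-week clock.

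Much of this stands. A reader might infer that PDR001 may never be held for Grade 2 colitis, or that Table 6-9 alone lacks a Grade 2 hold. The documents support neither: the indirect routes are real, and Table 6-20 also has no hold in its mandatory column. Nor is uneven clock wording peculiar to colitis.

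What does not stand is that the general text settles the matter. Table 6-8 sends diarrhea/colitis to Table 6-9, and the mandatory column there says to continue. Rash and hand-foot reaction have their hold written into their own tables; colitis does not. A clock that starts only when an investigator chooses to hold makes a compulsory stopping rule depend on discretion.

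**Conclusion.** The point holds in limited form. Grade 2 colitis without persistent Grade 2 diarrhea has no colitis-specific mandatory hold for PDR001, while the eight other graded non-hematologic tables of Section 6.3.3 each give Grade 2 a hold. The missing clock start is a secondary consequence.

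This rests on reading the page-split row as one row with a single mandatory cell, which is how the table is laid out. The 18% is an illustration under the stated assumptions, not an estimate of risk; a reader might take it as a rate of harm, but the protocol has no episode frequency to support that. Exposure is small: at most 91 subjects, fewer on PDR001, and about 5 to 6 cycles to the planned end of follow-up. No endpoint, sample size or error rate is touched. It is a cheap safety clarification worth making.

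**What to change.** In the Grade 1-2 row of Table 6-9, add Grade 2 colitis as an interruption trigger for PDR001/placebo, held until Grade 1 or lower. State that the 12 weeks run from identification of the Grade 2 event, as Table 6-12 does. The clinical team should decide whether dabrafenib and trametinib are held as well.

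The cost is one trigger and one clock line in a single row, plus some additional short PDR001 interruptions. Amendment 7 made edits of this kind to Tables 6-13, 6-17 and 6-18. The completed PFS analysis is unaffected. If treatment continues through an extension phase under post-trial access (Section 6.1.5), the corrected row should be the one carried forward.
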